As these patient questionnaires cannot be linked to other study data, the patients will be asked to provide the following background information about themselves: age, gender, level of education, employment, location of practice (region in Denmark) and area examine with POCUS during the consultation (abdomen, heart, lung, musculoskeletal, gynaecological).

GP registration of possible adverse events: (outcome S7)

For the registration of possible adverse events, we will use a questionnaire giving the GPs the possibility to explain in free text using their own words to explain (1) what was scanned, (2) circumstances surrounding the scan, (3) what happened, and (4) reflections after the scan. This reporting of cases will be anonymous. Data will be collected from the educational intervention to the end of the study. We will report the aggregated total number of monthly registrations for each participating GP. The free text elaborations will not be reported, but passed on to the safety committee (see section 5d). The registration of adverse events for the study does not substitute the GP's registration of untoward incidents required by Danish law (<https://stps.dk/da/ansvar-og-retningslinjer/vejledning/rapporteringspligt/>).

Evaluation of the patient pathway and quality of selected POCUS examinations: (outcome S8)

After the study (July 2024), participating GPs will be instructed to make an evaluation of the patient pathway following selected POCUS examinations. A separate protocol will be developed for this part. The GPs will be asked to make a registration for each patient, who has been examined with a specific POCUS examination. Based on information found in the medical record the GP is asked to register the following information for each patient: (1) If the patient had subsequent imagining following the index consultation where POCUS was used by the GP, (2) if the patient was later re-examined for the same health complaint by the same GP, (3) if the patient was later re-examined for the same health complaint by another physician, (4) if the diagnosis at the index consultation was used was later confirmed or dismissed, (5) if the ultrasound findings in the index consultation was later confirmed or dismissed, (6) if there were any adverse events identified that were related to the POCUS examinations or the following course for the patient.

Background characteristics of participating GPs

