At baseline the following participant characteristics will be collected in a baseline questionnaire: Age (years), gender (M, F, other), seniority (year of graduation from medical school), experience (years working as a GP), previous use of ultrasound (number of years with regular use), previous ultrasound training (yes/no), scanner type (low range, mid range, high end), practice owner (yes, no), type of practice (collaboration, partnership, solo), location of practice (urban, rural, mixed), distance to the nearest imaging facility, number of patients assigned to the practice, and number of GPs working in the practice. In addition, we will register GP's participation in educational activities during the educational intervention.

Characteristics of scanned patients

From PLSP, we will receive the aggregated data (age, gender) on patients, who have had a POCUS fee-specific code registered in their medical record during the study. Age and gender are calculated based on patient ID in the medical records in the clinics (CPR numbers). These data are extracted and transferred to CAM AAU anonymously.

The collected characteristics of participating GPs and scanned patients will be used to describe the population and to do sensitivity analyses.

13 Time schedule

Approval of the study by Danish Regions and PLO: June 2022

Allocation of clusters: June 2022

Recruitment: June – September 2022

Registration of the study in Clinical Trials: October 2022

Participant allocation: October 2022

Ethical approval: November 2022

Data collection: (Time of data collection for each cluster is illustrated in Figure 2).

- Retrospective data collection using register data (Primary outcome P1 and P2 and secondary outcome S2 and S5): January 2023 – June 2024.
- Prospective data collection using GP questionnaires (Secondary outcome S2-S4): November 2022 – May 2024.
- Prospective data collection using patient questionnaires (Secondary outcome S6 and S7): June 2023 – June 2024
- Prospective data collection using GPs' registration of unwanted cases (outcome S8): January 2023 – June 2024.

- Background characteristics on participating GPs are collected at the first teaching seminar: January 2023 – January 2024.
- Retrospective evaluation of medical records are collected in July – October 2024.

Cleansing of data and data analysis: July 2024 – December 2024

Reporting of the study: 2025

14 Sample size

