The principal investigator (CAA) will monitor the data collection and contact the project steering committee in case of problems related to data collection or the validity of the collected data. The principal investigator (CAA) will also contact the steering committee in case of participant drop-out.

21b Description of any interim analyses and stopping guidelines, including who will have access to these interim results and make the final decision to terminate the trial

n/a

22 Harms

Ultrasound examinations are safe to perform on patients and radiation-free procedures⁴⁵.

Previous studies have found high diagnostic accuracies of POCUS examinations in the hands of generalists such as GPs⁴⁶. Still, introducing a diagnostic test may lead to an increased number of incidental findings and possible over-detection and overdiagnosis. A previous review of 564 medical records from patients examined with POCUS in Danish general practice did not reveal any adverse events related to POCUS use (unpublished data). However, patients generally put a lot of emphasis on diagnostic tests. Hence, the GPs are taught how to communicate the limits of their POCUS examination to patients to avoid false expectations and false reassurance.

The participating GPs will be obliged to report any Suspected Unexpected Serious Adverse Reactions (SUSARs), Serious Adverse Events (SAEs) and Adverse Events (AEs) related or possibly related to the use of POCUS to the adverse event committee. This reporting does not substitute the GP's registration of untoward incidents required by Danish law (<https://stps.dk/da/ansvar-og-retningslinjer/vejledning/rapporteringspligt/>).

23 Auditing

n/a

Ethics and dissemination

A minority of Danish GPs (12%) are already using POCUS in general practice. They have assembled their POCUS education individually and they are using POCUS very differently¹². This study aims to explore the effects of a tailored educational program for GP, framing specific evidence-based POCUS examinations to the general practice context. All scanning modalities included in the curriculum have previously been tested and evaluated in Danish general practice. Focused POCUS use in general practice has the potential to lead to faster and more precise diagnosis for patients seen in general practice.

24 Research ethics approval

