The study will be performed in accordance with the Declaration of Helsinki. The project was notified to the regional ethical committee (The North Denmark Region Committee on Health Research Ethics, registration number 96036), who responded that do ethical approval was necessary. The project is registered and conducted according to the regulations of the Danish Data Protection Agency (registration number 2022-068-03601).

25 Protocol amendments

Any modifications to the protocol that will impact the conduct of the study such as study objectives, study design, patient population, sample sizes, study procedures or significant administrative aspects will be registered on clinicaltrials.gov.

26a Consent or assent

Informed consent form the participating GPs will be collected by the principal investigator prior to the study. Patients, who participate in the patient questionnaire are asked to provide consent to the collection and analysis of these data.

During the study (January 2023-June 2024) participating GPs will inform patients about the study by making a written description of the study available in the clinic (see attached patient information).

26b Additional consent provisions for collection and use of participant data and biological specimens in ancillary studies, if applicable

Prior to the collection of retrospective register data by PLSP, we will seek The North Denmark Region for permission to use of data from patients' medical records without patient consent based on Danish Law (*Sundhedsloven*).

27 Confidentiality

Personal information about participants consenting to participate will be stored on a secure server at Aalborg University. All data will be kept for 10 years after completion of the study which in accordance with The European Code of Conduct for Research Integrity.

28 Declaration of interests

The authors declare that they have no competing interests.

29 Access to data

During the educational intervention the educational teachers will have access to data on the online platform. Participants will during the educational intervention have access to their own data shared on the online platform. The following authors will have access to collected data stored at the secure server at Aalborg University (AR, MBJ and CAA).

30 Ancillary and post-trial care

Any participants patients who suffer harm from a GPs' trial participation will be eligible to seek compensation by The Patient Compensation Association.

31a Dissemination policy

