This document contains the statistical analysis plan for 'The POCUS IN PRACTICE study Implementation of point-of-care ultrasonography in general practice: A stepped wedge cluster randomized trial'. The aim is to clarify analyses for the intended analyses. Therefore, the statistical analysis plan has been completed prior to the completion of the data collection. The overall purpose is to estimate the effect of a POCUS intervention for general practitioners. In the primary research article, the following outcomes are reported.

The primary outcomes are:

- (P1) The number of registered reimbursement codes sent by the participating GP.
- (P2) The number of referrals send to secondary care by the participating GP.

The secondary outcomes are:

- S1. The number of consultations in primary care (e-mail, telephone, video, visits) managed by the participating GP.
- S2. The GPs' perceived stress (Cohen's 10-item Perceived Stress Scale)
- S3. The GPs' job satisfaction (Warr-Cook-Wall Job satisfaction Scale)
- S4. The GPs burnout symptoms (Maslach Burnout inventory)
- S7. To describe the number of adverse events reported by the participating GPs following the intervention

The tertiary outcome is:

- T3. GPs' experiences of POCUS' influence on perceived stress, job satisfaction and burnout symptoms after the intervention.

The analysis intended for outcomes S5, S6, S8, T1 and T2 will not be specified in this statistical analysis plan, as these outcomes will be specified in elaborating study protocols and reported in separate articles.

The study design involves random and sequential crossover of clusters from control to intervention until all clusters are exposed (1). Participants (General Practitioners) have been recruited from 24th June 2022 to 1st September 2022 representing all five Danish regions. The GPs have been randomized to receive an education at different time-points.

2. Background of the trial

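### S7 adverse event collection closes in the last month of counted scans, so the primary article's harms count has almost no follow-up for late scans, and the plan does not say whether reporting and the safety committee continue through the July–October 2024 record review

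*Protocol*

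**What the plan says.** Protocol section 12 sets the S7 window: "Data will be collected from the educational intervention to the end of the study". Section 13 dates it: "Prospective data collection using GPs' registration of unwanted cases (outcome S8): January 2023 – June 2024". The label S8 there is a slip, since sections 7 and 12 define GP-reported adverse events as S7; section 13 attaches S7 to the patient questionnaires instead. SAP 5.2 defines S7 as the total reported by GPs during the study, by type of examination.

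The end of the study can be read from two places. Section 26a has "During the study (January 2023-June 2024) participating GPs will inform patients about the study". Section 12 introduces S8 with "After the study (July 2024), participating GPs will be instructed to make an evaluation of the patient pathway following selected POCUS examinations". Scan codes are counted to the same month, June 2024 (SAP 5.1).

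The S8 review asks, as its sixth item, "if there were any adverse events identified that were related to the POCUS examinations or the following course for the patient". Section 13 gives its timing: "Retrospective evaluation of medical records are collected in July", running to October 2024. Its details are left to a separate protocol, and the SAP's opening section states: "The analysis intended for outcomes S5, S6, S8, T1 and T2 will not be specified in this statistical analysis plan". The SAP sends these outcomes to separate articles.

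On the harms themselves, section 22 says "introducing a diagnostic test may lead to an increased number of incidental findings and possible over-detection and overdiagnosis", and adds that GPs are taught to avoid giving false expectations and false reassurance. The same section obliges GPs to report any event related or possibly related to POCUS to the adverse event committee. Section 5d gives the safety committee all reports of adverse events. Neither section states when this ends.

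**The concern.** The harms in section 22 mostly become visible after the consultation: an incidental finding leads to further work-up, a diagnosis is later dismissed, or a disease the scan seemed to exclude appears. S8 is built on this, because it asks whether the diagnosis and the scan findings were later confirmed or dismissed. S7 has no such allowance. It stops in the month of the last counted scans, with no run-out.

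The primary article will report S7 but not S8. It could therefore show few adverse events while the trial's own record review, published elsewhere, holds more. The protocol's background says that safety data on broad implementation are lacking and presents this surveillance as a contribution. The note to Figure 1 says that possible larger-scale implementation depends on the results. A reader of the primary article should be able to see how far its harms count reaches.

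**Working it through.** **1. Dates side by side.**
- S7 reporting: January 2023 to June 2024 (Protocol 13).
- Scans counted: to June 2024 (SAP 5.1).
- Record review: July to October 2024, after the study (Protocol 12 and 13).

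The gap between the last counted scan and the close of S7 is less than one month. Any event recognised after June 2024 falls outside S7 as SAP 5.2 defines it.

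**2. Where a late event can go.**
- *Into S7:* no. No sentence adds events from the sixth S8 item to S7.
- *Into S8:* yes, for selected examinations only.
- *To the safety committee:* the general duty in section 22 covers it, with no stated end date. However, the one reporting channel described is the online form in section 18a, and section 13 dates its collection to June 2024. The S7 text says that free text is passed to the committee; the S8 text has no matching sentence. The plan does not say whether the duty, the form and the committee continue through the review.

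**3. Exposure arithmetic (illustration).** Number the months as in Figure 2, with October 2022 = 1 and June 2024 = 21. First course months for clusters 1 to 10, as the figure reads in the extracted text, are 4, 5, 5, 6, 7, 8, 9, 10, 11 and 12.

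Window for a cluster = 21 − first course month + 1, which gives 18, 17, 17, 16, 15, 14, 13, 12, 11 and 10. The sum is 143 cluster-months.

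Assume even scanning in every cluster. The share of scans in the last d months is 10d/143 for d up to 10. This is also the share whose events would be recognised after June 2024 if every event came to light exactly d months after the scan.

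| d (months) | From first course month, 10d/143 | From the month after the third course month, 10d/113 |
|---|---|---|
| 1 | 10/143 = 7% | 10/113 = 9% |
| 3 | 30/143 = 21% | 30/113 = 27% |
| 6 | 60/143 = 42% | 60/113 = 53% |

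The second column takes three months off each window: 143 − 30 = 113. By cluster at d = 3, on the first basis, the share is 3/18 = 17% in cluster 1 and 3/10 = 30% in cluster 10. If scanning grows over time, all of these shares rise.

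**4. Effect of a four-month run-out (July to October 2024).** The remaining share is 10(d − 4)/143 for d above 4, and nil otherwise. At d = 1 and d = 3 it is nil. At d = 6 it is 20/143 = 14%, down from 42%.

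**5. What cannot be computed.** The documents give no time from scan to recognised harm, no expected event rate in the study and no expected number of scans. The values of d are assumptions, and the number of missed events cannot be derived.

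**The case against.** The strongest reply is that the trial already looks for late harms. The S8 review asks directly about adverse events and about dismissed diagnoses and findings. The GPs who carry it out are under the section 22 duty, and reporting required by Danish law continues alongside. A reader might infer that late harms are lost to the trial, or that the safety committee has no route to them. The documents support neither. S8 collects late events for selected examinations, the section 22 duty is open-ended as written, and the separate S8 protocol, not among the documents, could set out a route. What remains is that late events are outside S7, and that the present text does not say whether the duty and the committee run through the review.

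Second, the loss may be small. Section 22 cites an unpublished review of 564 records with no POCUS-related adverse events; by the rule of three, the 95% upper limit is about 3/564 = 0.5%. A reader might also take the 7%, 21% and 42% as lost events. They are shares of scanning time under assumed delays, and nothing more. Overdiagnosis can also rarely be recognised in a single patient, so a longer window would add little there.

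Third, the shorter windows of late clusters might suggest a biased comparison. S7 is purely descriptive, with no planned test between clusters or periods, so this has little analytic weight.

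Fourth, extending the form has problems of its own. The record review may prompt reports and so change how events are found; the form fields listed in sections 12 and 18a contain no scan date; and S7 reports are anonymous, so overlap with S8 cannot be removed. These points are right, and they shape the fix. Spontaneous reporting and structured review can properly remain two separate counts.

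**Conclusion.** The point holds for the S7 count and for the primary article that reports it. S7 closes in the last month of counted scans, with no run-out for harms recognised later. It does not hold as a claim that the trial ignores late harms or that the safety committee is shut out; on the committee, the plan is unclear rather than deficient.

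The exposure affected is 7% to 42% of scans for assumed delays of one to six months, given even scanning from the first course month and Figure 2 as it reads in the extracted text. The number of events is unknown and may be very small. By last scans is meant the last counted scans, since nothing says that GPs stop scanning in June 2024. This is a cheap improvement to the harms report, and it leaves the primary outcomes untouched.

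**What to change.** - **Protocol 12 and 13, SAP 5.2:** keep the S7 form open to October 2024 for events from scans made up to 30 June 2024. Add a scan-month field to the form. Show reports received after June 2024 on a separate line from those received during the study, because the record review may prompt them.
- **Protocol 5d and 22:** state that the reporting duty and the safety committee continue through the record review and cover events found under the sixth S8 item. This is mainly clarification; the S8 protocol should say the same.
- **Primary article:** if S8 adverse events are available when it is written, cite them beside S7 with the number of records reviewed. Do not add the totals, because the S7 reports are anonymous.
- **Protocol 13:** correct the labels, so that GP registration of unwanted cases is S7 and the patient questionnaires are S6 only.

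Cost: one existing online form stays open four months longer with one extra field, and the report gains a table line and a few sentences. Data cleaning and analysis already run to December 2024 (Protocol 13). The S7 table closes about four months later, and events recognised more than four months after June 2024 are still missed.

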The researcher cleaning the data set and responsible for analyzing the primary outcome will have no knowledge of participants. He is a researcher with a physiotherapy background.

Data collection, management, and analysis

18a Data collection - Plans for assessment and collection of outcome, baseline, and other trial data

Data will be collected at different timepoints (see Figure 2).

Register data: Data regarding different POCUS examinations, number of referrals, number of consultations will be delivered by PLSP (outcomes P1-P2, S1 and S5). The data are registered prospectively by participating GPs in the medical records during from October 2023 to June 2024. We will receive these data retrospectively from PLSP, who will use an algorithm to collect monthly aggregated data for each participating GP. Due to availability of reimbursement codes in the medical record system, primary outcome P1 is collected in months 3-21, while primary outcome P2 and S1 is collected in months 1-21.

From PLSP, we will receive the following aggregated data on patients (age, gender) calculated based on patient ID in the medical records in the clinics (CPR numbers). These data are extracted and transferred to CAM AAU anonymously.

GP questionnaire: For the cross-sectional questionnaire exploring burnout, stress and job satisfaction before and after the educational intervention, an online questionnaire will be distributed by email to participants and a possible reminder will follow after two weeks. The questionnaire will be collected through SurveyXact (Rambøll, Aarhus, Denmark).

The questionnaire collecting background characteristics on participating GPs will be collected on the first teaching seminar using a QR code to an online questionnaire SurveyXact (Rambøll, Aarhus, Denmark).

At the teaching sessions, participating GPs will be taught how to report AE and SAE related or possibly related to the use of POCUS as well as near-miss cases. These events will be reported as anonymous cases to the study adverse event committee in an online questionnaire specifically designed for this purpose. The participants will have a link for an online questionnaire in SurveyXact (Rambøll, Aarhus Denmark) where they will register: (1) Type of POCUS, (2) indication for the examination, (3) description of the event, (4) participant's reflections after the events and (5) questions for the adverse events committee.

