5.2 Secondary outcomes

Outcome S1:

The number of monthly consultations will be summarized for each participating GP from October 2022 to June 2024. In a stepped wedge analysis model, we will compare the number of consultations sent from primary care BEFORE the intervention to the number of referrals sent AFTER the intervention.

Outcome S2:

We will summarize each participating GPs' answer to stress-related items in the BEFORE and AFTER questionnaire, to calculate the Cohen's PSS sum score (PSS-score).

We will report the mean(SD) or median [IQR] PSS-sum score BEFORE and AFTER for all participating GPs. In addition we will report the frequency of GPs with a PSS sum score ≥ 18 BEFORE and AFTER indicating a high level of stress (2).

Outcome S3:

We will summarize each participating GPs' answer to Job satisfaction-related items in the BEFORE and AFTER questionnaire, to calculate the Warr-Cook-Wall Job satisfaction sum score (WCW-score).

We will report the mean (SD) or median [IQR] WCW-sum score extracted from the 9 sub-items as well as the score of the one overall item BEFORE and AFTER for all participating GPs. In addition, we will report the frequency of GPs with a WCW-sum score ≤ 3 BEFORE and AFTER indicating low job satisfaction (2).

Outcome S4:

We will summarize each participating GPs' answer to burnout-related items in the BEFORE and AFTER questionnaire, to calculate the sum score of the three dimensions in the Maslach Burnout inventory (emotional exhaustion (9 items), de-personalization (5 items), and personal accomplishment (8 items)) (2).

We will report the mean(SD) or median [IQR] sum score for each dimension BEFORE and AFTER for all participating GPs.

Outcome S7:

We will summarize the total number of adverse events reported by the participating GP during the study in relation to the type of ultrasound examination performed.

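### No step is planned to separate near-misses, AEs and SAEs in outcome S7, so its count can be inflated by non-harm events and does not show the number of SAEs

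*Protocol*

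**What the plan says.** **What is reported, and how.** Protocol section 18a has GPs "taught how to report AE and SAE related or possibly related to the use of POCUS as well as near-miss cases". It continues: "These events will be reported as anonymous cases to the study adverse event committee in an online questionnaire specifically designed for this purpose". Section 22 obliges GPs to report SUSARs as well as "Serious Adverse Events (SAEs) and Adverse Events (AEs) related or possibly related to the use of POCUS to the adverse event committee". Near-misses are not mentioned in section 22.

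**What the form asks.** Section 18a lists five items, beginning "1) Type of POCUS, (2) indication for the examination, (3) description of the event" and ending with the GP's reflections and questions for the committee. Section 12 describes the form as free text covering "1) what was scanned, (2) circumstances surrounding the scan, (3) what happened, and (4) reflections after the scan".

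**What is counted.** Section 12 says: "We will report the aggregated total number of monthly registrations for each participating GP". On the narratives it says: "The free text elaborations will not be reported, but passed on to the safety committee". SAP 5.2 says of S7: "We will summarize the total number of adverse events reported by the participating GP during the study", broken down by type of ultrasound examination. SAP 6.2 takes the GPs' reports from the survey tool as Excel files, and SAP 9 gives S7 descriptive statistics only.

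**The committee.** Protocol section 5d and SAP 8 have a safety committee handle the AE and SAE reports. SAP 8 adds that it had the mandate to end the trial.

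**The concern.** Reports of very different gravity enter through one channel, and the planned table has no column that tells them apart. Followed as written, the protocol's rule makes a near-miss and a serious event each add one to the same number. The SAP then calls a number from the same source adverse events.

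This matters for what S7 is meant to do. The protocol's introduction says that safety data on broad implementation are lacking, and it justifies surveillance as a way of finding scan types that carry risk. A count by scan type that mixes non-harm with serious harm serves that aim poorly: a scan with many near-misses would rank above one with few but serious events. The note to Figure 1 adds that the 2025 collective agreement may include wider implementation, depending on the results of the projects under the 2022 agreement. The S7 figure may therefore be read by people deciding on roll-out.

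**Working it through.** The plan states no rate, sample size or error level for S7, so there is no figure to reproduce. The check sets the texts side by side.

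1. **Categories that can be reported.** Section 18a: near-miss, AE, SAE. Section 22: SUSAR, SAE, AE. The two lists share AE and SAE. Near-miss appears only in the first and SUSAR only in the second.
2. **Channels.** One questionnaire serves everything in the section 18a list.
3. **Items that would separate the categories.** Section 18a lists five items (type of POCUS, indication, description, reflections, questions), none of them class or seriousness. Section 12 lists four (what was scanned, circumstances, what happened, reflections), again none.
4. **Breakdowns of S7.** Protocol: by GP and month. SAP: by type of examination. By seriousness or harm: none in either document.
5. **Classification step.** The committee receives the reports. Neither document says that it assigns a class or returns one to the analysis. SAP 6.2 describes an extract of GP reports with no coding step after it.

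Now let N, A and S be the numbers of near-miss, AE and SAE reports.

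- Protocol S7 counts registrations, so it equals N + A + S.
- SAP S7 equals N + A + S if every extracted report is counted. It equals A + S if adverse event is taken in its ordinary sense. The second reading needs someone to sort the reports, and no rule or field for that is given.
- The ratio of the two is (N + A + S)/(A + S). This is 1 when N = 0 and greater than 1 otherwise, so mixing can raise the count but never lower it.
- On either reading S is not shown separately.

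The documents give no value for N, A or S, so no inflation factor can be stated.

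**The case against.** The strongest reply is that the SAP governs the analysis and speaks of adverse events, not registrations, so near-misses would ordinarily be left out. They are named in only one sentence of the protocol. This has some force, and it is why the count *can* be inflated rather than *will* be. It does not settle the matter: the SAP gives the analyst no rule or field for removing near-misses, and the protocol's own rule counts all registrations. Nor does it supply the number of SAEs.

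Second, the form itself is not reproduced, only two short lists of its content, and the event description would let the committee sort cases. This is correct. Separation is unplanned, not impossible, and the remedy uses that fact.

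Third, S7 is not the only safeguard. The committee handles all AE and SAE reports, and S8 asks GPs to look for POCUS-related adverse events in medical records. Both points stand. However, S8 covers selected examinations after the study and is left to a separate protocol and article, and the committee's work has no stated output in S7.

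Fourth, sections 18a and 22 need not conflict, since training may be wider than an obligation. That is fair. The difference needs a sentence saying which set S7 counts; it is not a contradiction.

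Finally, S7 is secondary, descriptive and collected only from the intervention onward, with no group comparison planned. This limits the weight of the point but does not remove it.

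**Conclusion.** The point holds in a limited form and should be corrected. As planned, the S7 count can be inflated by reports of events without harm, by an amount that the documents do not allow one to estimate, and it does not show how many SAEs were reported. This rests on the two lists being a fair account of the form and on there being no unwritten classification step. The primary outcomes and all tested comparisons are untouched.

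A reader might infer more than the documents support:

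- *That S7 could be misstated in either direction.* Including near-misses can only add to the count. SAEs merged into a total are lost detail, not an understatement of it.
- *That mixing the classes spoils a comparison with the 564 reviewed records without adverse events (section 22).* Those came from record review, whereas S7 is self-report with no reviewed-record denominator. Classifying S7 would not make the two comparable.
- *That the split by scan type rests on withheld text.* Not reporting the narratives most naturally means not publishing them. Section 18a lists type of POCUS as an item, and SAP 6.2 extracts the reports.
- *That the total is some definite multiple of the true one.* Any such factor would only restate an assumed near-miss share.
- *That serious harm would go unnoticed.* The committee and S8 are there to detect it.

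**What to change.** In SAP 5.2, state that the safety committee classifies each report as SAE, AE, near-miss or unclassifiable, that S7 is reported as separate counts by class and scan type, and that only AEs and SAEs are counted as adverse events. The committee already receives these cases, so the cost is one recorded code per report and a sentence or two in the SAP.

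Where the form can still be changed, add closed fields for event class and scan type. This cannot be the whole remedy: protocol section 13 has the registration of unwanted cases running from January 2023 (listed there under S8), and the SAP describes the committee's set-up in the past tense, so reports may already have been filed without these fields.

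Also reconcile the two lists of form items in sections 12 and 18a, and the reportable categories in sections 18a and 22, including where SUSARs belong.

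The downside is a little more recording by the committee. Because reports are anonymous, the GP may not be reachable for missing detail, so some earlier reports may stay unclassifiable. Their number should be shown.
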